### 3. CHARACTERISTICS OF RESEARCH POPULATION

#### I. *Sample Size Justification:*

Assuming normality of the data, we calculated the statistical power assuming effect size 0.3 that is the difference in proportions of people who change their score in their follow-up. We also assume a standardized normal (Z) distribution for one sided test, we aim to achieve 80 % of the power fixing the type one error (alpha) level at 0.05 and we repeated the calculation under different assumption of score changing proportions at each group.

P1	P2	$\alpha$ ( Type I error )	$1 - \beta$ ( power )	Each Group	Total
0.1	0.4	0.05	0.80	25	50
0.05	0.35	0.05	0.80	21	42
0.01	0.30	0.05	0.80	19	38

From the table, we expect that our study will have an enough power to detect the true difference with at least 80% of probability with 25 samples for each arm even allowing less conservative score change proportions. The sample size determined also accounts for screen failures. The total number of subjects to participate in the study is 50.

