## II. Data Analysis and Monitoring

Descriptive statistics will be provided to compare baseline distribution of two groups, those who are treated by a traditional method and those who are treated by Cortisone for Baker's Cyst. Basically, we are comparing the change of scores in two groups in this study: a matched T-test (for a continuous score) or a chi-squared test (for a discrete score) or using non-parametric tests, Wilcoxon rank test and/or Kruskal-Walis test. The type of test will be decided after we check the normality of score distributions using Kolmogorov-Smirnov test or Shapiro-Wilks test.

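### The test for each score is chosen after the outcome data are seen, by either of two normality checks with no rule for which governs; one method per score should be named in advance.

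*Combined protocol and SAP*

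**What the plan says.** All of the plan's rules for choosing a test are in section 4, II. Data Analysis and Monitoring.

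- The quantity of interest is a change: "we are comparing the change of scores in two groups in this study".
- The candidate methods are "a matched T-test (for a continuous score) or a chi-squared test (for a discrete score) or using non-parametric tests, Wilcoxon rank test and/or Kruskal-Walis test".
- Choosing among them comes later: "The type of test will be decided after we check the normality of score distributions using Kolmogorov-Smirnov test or Shapiro-Wilks test".

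The section does not state the significance level of the check, or whether Kolmogorov-Smirnov is corrected for an estimated mean and SD. It does not say whether arms are checked separately or pooled, whether raw or change scores are checked, or what happens if the checks disagree. No other section settles these points. The sample size section only makes a planning assumption: "Assuming normality of the data".

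**The concern.** Three choices are left open in sequence: which normality check to run, which family of tests follows from it, and which member of the fallback, "using non-parametric tests, Wilcoxon rank test and/or Kruskal-Walis test", to report. All are made once the outcome data exist. A t-test compares means and a rank test compares ordering, so the question answered can differ between scores for reasons unrelated to the trial's aims.

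The opening recurs. VAS, five KOOS domains and cyst size are continuous or nearly so, and each is measured at two follow-up visits: 7 × 2 = 14 comparisons before the clinical grade is counted. No primary outcome or time point is named.

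Nothing in the plan keeps the person choosing the test from knowing the results. Blinding is described for the patient only. The principal investigator is also the study monitor and discusses accumulating findings with the team each quarter.

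At stake is whether a reported p-value belongs to a test fixed beforehand.

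**Working it through.** **1. The plan's own figure.** The sample size section takes an "effect size 0.3 that is the difference in proportions of people who change their score in their follow-up", states "We also assume a standardized normal (Z) distribution for one sided test", and works by "fixing the type one error (alpha) level at 0.05" with 80% power. With p̄ = (P1 + P2)/2,

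n per arm = [1.645·√(2p̄(1−p̄)) + 0.842·√(P1(1−P1) + P2(1−P2))]² / (P2−P1)²

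- 0.1 v 0.4: (1.007 + 0.483)²/0.09 = 24.7, so 25
- 0.05 v 0.35: (0.930 + 0.441)²/0.09 = 20.9, so 21
- 0.01 v 0.30: (0.842 + 0.395)²/0.0841 = 18.2, so 19

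All three rows reproduce. This calculation concerns proportions and does not bear on the choice of test for a score, except that it fixes 25 per arm.

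**2. How often the checks disagree.** The documents give no disagreement rate and no distribution, so every scenario is assumed. Trials of 25 per arm were simulated, with each check at 0.05 and normality rejected if either arm rejected. Uncorrected Kolmogorov-Smirnov (KS) uses the estimated mean and SD with standard p-values; Lilliefors is the corrected version.

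| Score checked | Shapiro-Wilk v uncorrected KS | Shapiro-Wilk v Lilliefors |
|---|---|---|
| VAS change, 0.1 steps | 9-12% | 10-13% |
| KOOS change | 8-13% | 13-18% |
| VAS change, whole numbers | 21-24% | 32-34% |
| Grade 0-3 change | 57% | 0.3% |
| VAS change, responder mixture | 62-84% | 2-16% |
| Raw follow-up scores | 31-92% | 0-39% |

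A benchmark: on truly normal data, Shapiro-Wilk in two arms rejects at least once in 1 − 0.95² = 9.75% of trials, while uncorrected KS almost never rejects. The simulated disagreement there was about 9-11%. For near-continuous change scores, the bounds of the scale therefore add little.

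A second set of VAS-change scenarios (baseline mean 5.5, SD 2; follow-up mean 3, SD 2.2; clipped to 0-10; correlation 0.3, 0.5 or 0.7; shift 0 or 1.6) shows how much rounding matters. Shapiro-Wilk and uncorrected KS disagreed in 22-48% of trials with whole-number VAS and 8-10% with 0.1 steps.

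**3. How often the conclusion changes.** The choice of check matters only where the checks disagree and the unpaired t-test and rank-sum test also differ at two-sided 0.05.

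- No effect: 0.1-3% (uncorrected KS), 0-0.9% (Lilliefors).
- With an effect: 0.9-15% (uncorrected KS), 1.0-2.8% (Lilliefors).
- In the second set, 0.1-1.7% over all scenarios.

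The largest value comes from VAS in 0.1 steps with 10% and 40% responders, the plan's own main pair of proportions. Shapiro-Wilk rejected in 87.5% of trials and uncorrected KS in 7.1%; they disagreed in 80.4%, and the verdict flipped in 14.7%. Power was 43.7% if Shapiro-Wilk governed and 55.1% if uncorrected KS did: 55.1 − 43.7 = 11.4 points, decided by which check was run.

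**4. Type I error.** Following the two-stage rule mechanically gave 4-6% in the no-effect mixture scenarios. Always taking the smaller of the t-test and rank-sum p-values gave roughly 5.5-7.5%.

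**5. What a named method gains.** Let r be the baseline to follow-up correlation. In the second set, before clipping, the SD of change is √(2² + 2.2² − 2·r·2·2.2) and the residual SD after baseline adjustment is 2.2·√(1−r²).

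- r = 0.3: 2.49 v 2.10; a 1.6-point shift is 0.64 v 0.76 SD.
- r = 0.7: 1.64 v 1.57; 0.98 v 1.02 SD.

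With clipping, simulated power was about 59-90% for the t-test on change and 74-93% for the baseline-adjusted model, with error near 5%.

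**The case against.** The plan does link the t-test to continuous scores and chi-squared to discrete ones, so it is not silent. That stands in part, but the next sentence makes the type of test depend on the normality check and so reopens the choice.

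The strongest objection concerns size. A reader might infer that the checks usually conflict on bounded scores, say in a quarter of trials or more. The documents do not support that. They give no VAS resolution, and the rate exceeds a quarter mainly under whole-number recording, responder mixtures, or raw follow-up scores. The plan says it compares changes, and near-continuous change scores gave 8-18%. Much of the high end also depends on uncorrected Kolmogorov-Smirnov, which the plan neither specifies nor excludes. This objection stands.

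A reader might also infer serious false-positive inflation. The 5.5-7.5% figure needs an analyst who always reports the smaller p-value, and the plan describes no such practice. Nor does the fallback's wording add much multiplicity: with two arms, Kruskal-Wallis is equivalent to the two-sided rank-sum test without continuity correction.

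Finally, naming any single test would cure the defect, so baseline adjustment goes further than strictly needed. That is true, but the baselines are already collected and the precision gain is real in the scenarios examined.

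**Conclusion.** The concern holds in limited form. The text is clear that the test is selected from the trial's own outcome data, by either of two checks with no rule between them and with an open fallback. The main harm is loss of prespecification and an unstable target of comparison, not a large error rate.

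Disagreement between the checks ranges from under 10% to over 80% of trials; flipped conclusions are rarer, at about 0-3% with no effect and about 0.3-15% with one. These rates are per comparison. They rest on assumed distributions, 25 per arm, checks at 0.05, and an unpaired t-test. The plan's matched t-test does not fit two independent arms; that is a separate matter. The gain from baseline adjustment depends on the assumed correlation and on how close the scores lie to the floor.

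This should be changed, but it does not by itself undermine the trial.

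**What to change.** In section 4, II. Data Analysis and Monitoring:

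1. Delete the normality gate.
2. For VAS and each KOOS domain, name a linear model of the follow-up score on arm and its baseline value. A robust-SE or permutation p-value may be specified if preferred. If cyst size is to be compared, name its method too.
3. For the Rauschning and Lindgren grade, name one rank or ordinal test.
4. Report any rank version of the continuous analyses once, labelled as sensitivity.
5. Drop Kruskal-Wallis as redundant with two arms.

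The cost is statistical wording only. The 25 per arm, the visits and the measurements are unchanged, and the baseline values needed are already in both schedules of events.

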## III. Data Safety Monitoring Plan (DSMP)

### I. Description of the types of data or events that will be captured

#### a. SAFETY information to be collected

All disease signs and symptoms experienced by the patient, as defined below as AE, TEAE, SAE, and UADE, will be recorded from questionnaires during each visit and clinic visits. Specific information collected about the adverse event will include the nature, date and time of the event. There will also be a determination of seriousness, frequency, severity, corrective treatment, outcome, and the principal investigator's opinion of the relationship to the Ultrasound guided aspiration and injection of either Corticosteroid or Platelet-Rich-Plasma. Documentation will begin at the time the patient signs the informed consent form to the completion of the final study visit.

- Adverse Event (AE)

An AE is any untoward or unfavorable medical occurrence in a patient involved in a study associated with the use of a medical treatment or procedure regardless of whether it is considered related to the treatment or procedure. AEs therefore include any undesirable physical, psychological or behavioral effect experienced by a subject during their participation in this investigational study, whether or not the effect is considered interrelated.

The Principal Investigator will assess relationship between the AE and study treatment according to the following definitions:

- Unrelated: There is no relationship between the AE and the use of the investigational device or any study treatment. This may include but is not limited to the incident being an expected outcome of a previously existing or concurrent disease, concomitant medication or procedure the patient experienced.
- Remote/unlikely: There is no clear relationship between the AE and the use of the device under investigation or study treatment and it is unlikely that there is some relationship.
- Possible: There is no clear relationship between the AE and the use of the study device or study treatment; however, one cannot definitely conclude that there is no relationship.

- Probable: While a clear relationship to the device under investigation or study treatment cannot be established, the AE is associated with an expected AE or there is no other medical condition or intervention, which could explain the occurrence of such an event.
- Definite: The relationship of the AE and the use of the study device or the execution of the study treatment can definitely be established.

- Treatment Emergent Adverse Event (TEAE)

A TEAE is defined as any event not present prior to the initiation of the treatment or any event already present that worsens in either intensity or frequency following exposure to the treatments. The assessment of TEAEs and their relationship to the study treatment will be assessed by the Principal Investigator.

- Serious Adverse Event (SAE)

A SAE is defined as any AE, irrespective of a possible relationship to the study device that results in any of the following outcomes:

- Death
- Life-threatening event
- Requires inpatient hospitalization or prolongation of existing hospitalization
- Results in persistent or significant disability/incapacity
- Congenital anomaly
- An important medical event defined as an AE that may jeopardize the subject and may require medical or surgical intervention in order to prevent one of the outcomes listed above

- Unexpected Adverse Device Effect (UADE)

A UADE is defined as any serious adverse effect on health or safety or any life-threatening problem or death caused by, or associated with, a device, if that effect, problem, or death was not previously identified in nature, severity, or degree of incidence in product labeling, the investigational plan or application (including a supplementary plan or application), or any other unanticipated serious problem associated with the study device that relates to the rights, safety, or welfare of subjects (21 CFR 812.3(s)).

b. Clinical Outcomes of Platelet Rich Plasma Injection versus Corticosteroid Injection for Baker's Cyst, information to be collected

- History and physical exam of the patient
- History and physical exam of the study lower extremity
- Concomitant medications
  - Type
  - Dose
  - Frequency
  - Duration
- Patient Outcomes Assessments
  - Visual analog scale (VAS) for rating activity-related pain
  - Rauschning and Lindgren criteria for rating clinical presence of Baker's cyst
  - Knee Injury and Osteoarthritis Outcome Score (KOOS) for rating outcome of knee related conditions
    - Ultrasound of Study Lower extremity
- Reportable and/or adverse events

II. Plan for assuring data accuracy and protocol compliance

Study Monitor

The Principal Investigator for this study will also serve as the Study Monitor. He will conduct interim monitoring of accumulated data from research activities to assure the continuing safety of research participants, relevance of the study hypothesis, appropriateness of the study, and integrity of the accumulating data.

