**IV. Aims:**

- 1) To evaluate the outcome of baker's cysts with the use of Platelets-Rich-Plasma versus Corticosteroid
- 2) To evaluate the recurrence of baker's cysts treated on each group
- 3) To evaluate complications
- 4) To evaluate side effects

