An ultrasound guided aspiration and triamcinolone (40 mg) diluted with lidocaine without epinephrine and ropivacaine will be used to anesthetize the tissues down to the cyst(including within the cyst for steroid injections). A compression bandage will be placed locally for 7 days. Investigators will monitor any side effect from the injection and treat the patients per standard care, this can include prescription of analgesics.

Both groups will be asked to have a follow up after 3 months and 6 months of the day of the procedure with measurements of the dimensions of the baker's cysts with ultrasound, Visual Analogue Score, and Rauschning and Lindgren criteria and reclassification.

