## SCHEDULE OF EVENTS - CONTROL GROUP (Corticosteroid)

Description	Visit 1 (Baseline)	Visit 2 (12 Week)	Visit 3 (24 Week)
Study Visit Windows			
Informed Consent	x		
Complete Physical & Medical History	x		
Knee Assessment/Brief Exam	x		
Ultrasound	x	x	x
Aspiration and Steroid Injection	x		
Visual Analogue Score	x	x	x
Knee Injury and Osteoarthritis Outcome Score	x	x	x
Rauschning and Lindgren criteria	x	x	x

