**IV. Frequency of monitoring entity's assessment of data or events**

The study monitor will assess all safety data immediately as they occur. Study data will be assessed on a weekly basis.

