## 5. RISKS AND BENEFITS

### I. Risks:

Subjects involved in the study will be at risk of complications associated with the injection such as pain at the site of the injection, infection, bleeding or hematoma formation.

Subjects in the Corticosteroid group: Studies have shown that corticosteroid injection into soft tissues is safe, and no serious unexpected reactions have been reported. In general, corticosteroid injection into the cyst may result in local atrophy and post injection flare but the use of Triamcinolone lowers the frequency of these complications from happening due to its pharmacological characteristics.

Subjects in the PRP group: Although There has been no data about using PRP into a baker's cyst, studies have stated that the side effects of Platelets-Rich-Plasma injections in soft tissues are very limited as the patients are utilizing their own blood. The main risk includes local infection (less than 1%) and flare reaction beginning the day after the injection.

Breach of confidentiality is an unlikely, but possible risk to subjects included in this study.

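### No adverse-event contact is scheduled between the injection visit and week 12, so mild early events rest on about 12 weeks of recall unless the patient reports them unprompted

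*Combined protocol and SAP*

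**What the plan says.** Two of the four aims in Section 2.IV concern safety. Aim 3 is "To evaluate complications" and Aim 4 is the same for side effects.

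Collection is described in the Data Safety Monitoring Plan (Section 4.III, I.a). Signs and symptoms "will be recorded from questionnaires during each visit and clinic visits". The period is continuous: "Documentation will begin at the time the patient signs the informed consent form to the completion of the final study visit". The detail wanted is considerable: "Specific information collected about the adverse event will include the nature, date and time of the event", together with seriousness, frequency, severity, treatment and outcome.

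The two Schedules of Events have three columns: Visit 1 (baseline, which includes the injection), week 12 and week 24. Neither table has a row for adverse events. The text of Section 4.I agrees on timing: "Both groups will be asked to have a follow up after 3 months and 6 months of the day of the procedure". The items it then lists are ultrasound, VAS and the Rauschning and Lindgren grade.

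Section 5.I names pain at the injection site, infection, bleeding and hematoma for both arms, atrophy and flare for the corticosteroid arm, and infection and flare for the PRP arm. An onset is given for one of these, the PRP flare: "flare reaction beginning the day after the injection".

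On review, part IV of the monitoring plan says: "The study monitor will assess all safety data immediately as they occur". Sections 4.I and 5.II add that investigators will monitor and treat side effects in both arms.

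**The concern.** An event that begins and resolves within days of the injection, and is too mild to bring the patient back, meets no scheduled question until week 12. By then the patient may have forgotten it, or may remember it without a usable date, duration or severity. Events of this kind are a large part of what Aims 3 and 4 are meant to describe.

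This matters more than usual here because Section 5.I states that there are no data on PRP injected into a Baker's cyst. The trial's own safety record would be the evidence. If early events enter it mainly through patients who choose to call, the record reflects willingness to call as well as event frequency.

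**Working it through.** **Step 1: set the schedule against the stated onset.**

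| Item | Value | Source |
|---|---|---|
| Injection | Visit 1 | Both Schedules of Events |
| Next scheduled contact | Week 12 = 12 × 7 = day 84 | Both Schedules of Events |
| Onset of PRP flare | Day 1 | Section 5.I |
| Delay from onset to first scheduled question | 84 − 1 = 83 days | Arithmetic |
| Delay between later visits | 24 − 12 = 12 weeks = 84 days | Both Schedules of Events |

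The text of Section 4.I counts 3 months from the procedure itself, so the gap is about the same whichever passage is followed. The seven-day compression bandage and the two-week period without anti-inflammatory medication carry no scheduled return visit or call.

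**Step 2: look for another route by which an early event could arrive.**

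- Section 4.I (both arms) and Section 5.II promise monitoring of side effects, but give no time, contact or method.
- Part IV of the monitoring plan sets how quickly the study monitor assesses safety data. It governs data already received.
- Clinic visits are named as a source in I.a. They capture patients who come in.

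None of these is a solicited contact between discharge and week 12.

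**Step 3: the plan's own figure.** The documents contain no calculation for adverse events. The one computed figure used below is 25 per arm (Section 3.I). It reproduces with the pooled-variance formula, one-sided α = 0.05 and 80% power, for 0.1 v 0.4 (mean proportion 0.25):

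n = [1.645 × √(2 × 0.25 × 0.75) + 0.842 × √(0.1 × 0.9 + 0.4 × 0.6)]² / 0.3² = 24.7, rounded up to 25.

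The point does not depend on this result and does not change it.

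**Step 4: illustrate the loss.** The true flare rate p and the share of flares captured c are both assumptions; the documents give neither. With n = 25:

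- expected recorded events = 25 × p × c
- chance of at least one recorded event = 1 − (1 − p × c)^25

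| Assumed true rate p | c = 100% | c = 50% | c = 25% |
|---|---|---|---|
| 10% | 2.5 events; 93% | 1.25; 72% | 0.63; 47% |
| 20% | 5.0; >99% | 2.5; 93% | 1.25; 72% |
| 30% | 7.5; >99% | 3.75; 98% | 1.88; 86% |

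At an assumed true rate of 10%, losing three quarters of the flares makes it slightly more likely than not that the PRP arm reports none (100 − 47 = 53%). At higher rates some flares would still be seen, but the rate would be understated in proportion to c.

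**The case against.** The strongest reply is that the plan is not silent. Documentation runs from consent to the last visit, Visit 1 is itself a visit, and clinic visits can be read as including unscheduled ones. Investigators are to monitor and treat side effects, and concomitant medication is recorded. Events on the procedure day, and events that make a patient seek care, can therefore be recorded early. That stands. It limits the problem to mild events that the patient does not bring forward.

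It can also be said that the number of early contacts in a 50-patient, single-injection trial is a design choice, and that Section 4.II plans tests of score changes and no test of adverse events. Both are true. No planned test fails because of this gap. What suffers is the description of two stated aims.

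Some stronger readings are tempting, and the documents do not support them:

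- **That events are collected only at weeks 12 and 24.** The text covers every visit, including the injection visit, and clinic visits.
- **That all the named risks begin the day after injection.** That onset is stated for the PRP flare alone.
- **That the comparison between arms is biased toward no difference.** With equal capture, assumed rates of 20% v 5% at an assumed 40–80% recall become 8–16% v 2–4%. The difference shrinks from 15 points to 6–12, but the ratio stays at 4. If capture differs by arm, the bias can go either way. Patients are to be blinded, with a blood draw in both arms, which limits differential reporting.
- **That the stopping rule would be reached late.** Part V of the monitoring plan is triggered by SAEs or UADEs thought possibly related to treatment; a mild flare is neither.
- **That the gap explains why rare infections might be missed.** With 25 per arm that follows from the sample size even with full capture, and an extra contact would not change it.

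**Conclusion.** The point holds in a limited form. Solicitation is tied to study and clinic visits, neither schedule has an adverse-event row, and nothing is scheduled between the injection visit and week 12. A mild early event, of which the PRP flare is the plan's own example, is first asked about on schedule roughly 83 days after onset. Followed as written, the plan is likely to under-record and misdate such events, although they belong to Aims 3 and 4 and a date and time are required for each.

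The 83 days follow from the documents. The extent of under-recording cannot be derived from them, and the figures in the working rest on assumed flare rates and capture shares. Sample size, power and the planned score analyses are unaffected. This is an inexpensive improvement to data collection, and it does not invalidate the trial.

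**What to change.** 1. Add an adverse-event row to both Schedules of Events, marked at every visit.
2. Add one early solicited record in identical form in both arms, using the questionnaire already foreseen in Section 4.III, I.a. This can be either a scripted phone call by existing research staff in the first one to two weeks, or a two-week take-home symptom diary returned at Visit 2.
3. State that complications and side effects will be reported by arm from these records together with the visit records.
4. Reconcile part IV of the monitoring plan with the collection method, by saying how an event after discharge reaches the study monitor. The call is preferable for this purpose: a diary handed in at week 12 helps recall and dating but does not bring the information in sooner.

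The cost is about 50 short calls or diary cards and some coordinator time. No procedure, extra staff or change in sample size is needed.
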